### **3) Background**

Enterocutaneous fistula is (ECF) defined as an abnormal connection between the gastrointestinal tract and the skin, or an open abdomen (enteroatmospheric fistula, EAF). This disease is highly morbid and associated with significant ICU length of stay, hospital stay, and average hospital charges >\$500,000 [1]. Death and complication rates are disproportionately high, with mortality rates commonly reported between 6 to 48% [2]. Survivors with ECF have lower health-related quality of life [3].

The treatment of ECF is challenging and often requires a multi-disciplinary approach including gastroenterologists, surgeons, wound care specialists, and nutritionists. Intestinal rehabilitation for ECF is directed at decreasing ECF output (completely, if possible) and achieving independence from artificial nutrition (enteral or parenteral). There are few pharmacologic options for the treatment of ECF. Somatostatin and its analogues (ex: octreotide) have been the most widely studied, but results are conflicting, with significant effects being found only on meta-analysis [4].

Glucagon-like peptide 2 (GLP-2) is an endogenous hormone secreted by L cells in the intestine which has trophic effects. Exogenous GLP-2 administration stimulates intestinal blood flow, decreases gastric acid secretion, and improves nutrient and fluid absorption in animal models and human studies [5-7].

Teduglutide is a GLP-2 analogue with a much longer half-life than GLP-2. An open label pilot study of teduglutide demonstrated improvements in enteral absorption. At the microscopic level, improvements were seen in small bowel villus height, crypto depth, and mitotic index [8]. In two phase III randomized, placebo-controlled studies, 24 weeks of administration of teduglutide led to significant decreases in PN/IV volume requirements [9, 10]. Small bowel villus height and plasma citrulline (a marker for enterocyte mass) were both significantly improved in the teduglutide groups [9]. This efficacy was not only maintained, but also increased, in long-term extension studies with continued gains and

IRB Study Number: 20170189  
Version Date: June 16, 2021  
PI: [name]

NCT02889393

additional patients achieving PN/IV independence. Of the 19 non-responders in the original 24-week study, 11 became responders in the extension study [11]. Approved by the FDA in 2012 for the treatment of adults with short bowel syndrome with intestinal failure (SBS-IF), teduglutide is well-tolerated and common adverse events are mild and related to gastrointestinal symptoms such as abdominal pain, nausea, and vomiting [12].

It is easy to conceive that the results of teduglutide treatment could be extrapolated to patients with ECF. For example, SBS-IF patients treated with GLP-2 experienced a reduction in fecal wet weight of approximately 33% (from 3.0 kg/day to 2.0 kg/day) [7]. Similar changes in ECF could convert high-output fistulas (>500 mL/day) to medium- (200-500 mL/day) or low-output fistulas (<200 mL/day), significantly simplifying fluid/electrolyte management, or even resolve low-output fistulas completely.

#### **4) Entry Criteria**

##### **Inclusion criteria**

- a) Age >18
- b) Enterocutaneous fistula (ECF) that could be secondary to volvulus, injury, prior trauma or surgery, or vascular ischemia

##### **Exclusion criteria**

- a) Perianal fistula
- b) History of radiation enteritis or sprue (as defined by history)
- c) Active (<1 year) alcohol or drug abuse
- d) Significant hepatic, or cardiac diseases as defined as:
  - i. Hepatic: aspartate aminotransferase (AST)  $\geq 2$  times upper limit of normal (10-40 U/L)
  - ii. Cardiac: unstable angina or evidence of active myocardial ischemia (elevated troponin level drawn by clinical suspicion)
- e) Severe renal dysfunction: serum creatinine  $\geq 2$  times upper limit of normal (0.6-1.5 mg/dL)
- f) Received IV glutamine less than 4 weeks prior to screening
- g) Receiving growth factors (erythropoietin, granulocyte colony-stimulating factor, granulocyte-macrophage colony stimulating factor, and human growth hormone)
- h) Pregnancy or lactation (women of childbearing age will be excluded if they do not agree to either complete sexual abstinence during the study or if they refuse to use at least two forms of highly effective contraception such as oral contraception, injectable or implantable contraception, vaginal rings, or intrauterine devices (IUD))
- i) Active malignancy or suspicion for gastrointestinal malignancy on CT scan obtained during standard clinical care, if available
- j) Not capable of understanding or not willing to adhere to the study visit schedule and drug administration requirements

IRB Study Number: 20170189  
Version Date: June 16, 2021  
PI: [name]

NCT02889393

- k) First degree relative with history of intestinal malignancy (gastric, small intestine, colon)
- l) Personal or first degree relative with history of hereditary non-polyposis colorectal cancer, familial adenomatous polyposis, first degree relative with colon cancer
- m) Positive hemoccult (per rectum) obtained during standard clinical care, if available
- n) Abnormal baseline electrocardiogram (ECG) suggestive of congestive heart failure or underlying cardiac disease
- o) Taking oral benzodiazepines, barbiturates, or phenothiazines

## 5) Procedures Involved

Study team will screen the inpatient census and clinic roster of the “Surgical Nutrition” team at the University of Miami Hospital and identify potentially eligible subjects with enterocutaneous fistulas. If the patient meets all inclusion/exclusion criteria, a member of the study team will then approach the patient or surrogate. Re-screening of patients can be made at the PI’s discretion, if the patient meets all of the inclusion, and none of the exclusion criteria.

### **Eligibility Screening Visit(s):**

Screening procedures can be completed over several visits

Obtain informed consent

Demographics

Medical and surgical history

Review prior and concomitant medications

Collect Physical exam

Collect Vital signs measurements

ECG

Chemistry Panel (sodium, potassium, chloride, bicarbonate, blood urea nitrogen, creatinine glucose) if not done in the last 90 days

Liver Function tests (total bilirubin, direct bilirubin, alkalkine phosphatase, alanine aminotransferase, aspartate aminotransferase, lipase, amylase) if not done in the last 90 days

Serum pregnancy test if applicable

Collect Concomitant medical review

Collect Nutritional assessment

3-day average fistula output

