### **Enrollment within 2 months of signing consent**

Inclusion/Exclusion criteria

Vital signs measurements

Nutritional assessment

3-day average fistula output

Complete questionnaires (see additional documents):

1. ASCQ-Me Short Form v2.0 - Social Functioning Impact
2. ASCQ-Me v2.0 - Sleep Impact Short Form

IRB Study Number: 20170189  
Version Date: June 16, 2021  
PI: [name]

NCT02889393

3. Global Health Scale v1.2
4. PROMIS Scale v1.0 - GI Belly Pain
5. PROMIS Scale v1.0 - GI Diarrhea
6. PROMIS Scale v1.0 - GI Nausea and Vomiting
7. PROMIS SF v2.0 - Ability to Participate

Teaching of self-administration of medication

After study enrollment, the subject will be randomly assigned (by a computerized method, using the site 'www.sealedenvelope.com') to begin teduglutide treatment immediately or to continue standard of care (SOC) treatment. The randomization will be performed by a member of the study that is not involved in the informed consent process, and will be enclosed in sequentially numbered opaque envelopes. The envelopes will be given to the PI prior to the enrollment visit. At study visit 5 (day 56), the subject will then cross-over to the opposite treatment assignment. The half-life of teduglutide is 2-3 hours. During the period the subjects are on the "SOC only" treatment arm, the subjects will be given the option to replace some Study visits with Telephone Calls for their convenience. If study visits overlap due to the time window, either visit may be skipped or completed on the same day. Please see information below, and the Study schema.

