**Study Visit 3 (Day 28) (+/- 1 week)**

IRB Study Number: 20170189  
Version Date: June 16, 2021  
PI: [name]

NCT02889393

Collect physical examination  
Collect Vital Signs measurements  
Chemistry Panel (sodium, potassium, chloride, bicarbonate, blood urea nitrogen, creatinine glucose)  
Liver Function tests (total bilirubin, direct bilirubin, alkalkine phosphatase, alanine aminotransferase, aspartate aminotransferase, lipase, amylase)  
Plasma PK (Pharmacokinetics)

- Processed according to separate “Sample Processing Procedure”

Serum pregnancy test  
Monitor severe adverse events (SAE) and adverse events (AE)  
Collect Concomitant medication review  
Collect Nutritional Assessment  
3-day average fistula volume (3 days immediately preceding study visit)  
Collect adjustment of medications and fluids if recorded

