**Appendix E Treatment Schema**

	Eligibility / Screening	Enrollment	Treatment							Cross-over
			Day 7 Study Visit 1 +/- 3 days	Day 14 Study Visit 2 or Telephone +/- 3 days	Day 21 Telephone Call 1 +/- 3 d	Day 28 Study Visit 3 +/- 1 week	Day 35 Telephone Call 2 +/- 3 days	Day 42 Study Visit 4 or Telephone +/- 1 week	Day 49 Telephone Call 3 +/- 3 d	Day 56 Study Visit 5 +/- 1 week
Informed Consent	X	X								
Inclusion and exclusion criteria	X	X								
Demographics	X									
Medical and surgical history	X									
Review prior and concomitant medications	X									
Complete Physical Exam A	X		X	X		X		X		X
Vital signs measurements B	X	X	X	X		X		X		X
Self-administration of medication and teaching if needed		X	X	X	X	X	X	X	X	X
IP Dispensation and Accountability		X	X	X		X		X		X
Chemistry panel	X					X				X
Liver function tests	X					X				X
Plasma PK*						X				X
Serum pregnancy test	X					X				X
ECG	X									
Monitor SAE/AE C			X	X	X	X	X	X	X	X
Concomitant medication review	X		X	X		X		X		x
Nutritional assessment D	X	X	X	X	X	X	X	X	X	X
3- day fistula output	X	X	X	X	X	X	X	X	X	X
Questionnaires		X								X

IRB Study Number: 20170189  
 Version Date: June 16, 2021  
 PI: [name]

NCT02889393

	Treatment							End-of-Treatment	Long-Term Follow-up
	Day 63 Study Visit 6 or Telephone +/- 1 week	Day 70 Study Visit 7 or Telephone +/- 1 week	Day 77 Telephone Call 4 ± 3 d	Day 84 Study Visit 8 ± 1 week	Day 91 Telephone Call 5 ± 3 d	Day 98 Study Visit 9 or Telephone +/- 1 week	Day 105 Telephone Call 6 ± 3 d	Day 112 Study Visit 10 ±1 week	Study Visit 11 (3 months after EOT) -2wks to +3 mos.
Informed Consent									
Inclusion and exclusion criteria									
Demographics									
Medical and surgical history									
Review prior and concomitant medications									
Complete Physical Exam A	X	X		X		X		X	
Vital signs measurements B	X	X		X		X		X	
Self-administration of medication and teaching if needed	X	X	X	X	X	X	X		
IP Dispensation and Accountability	X	X		X		X		X E	
Chemistry panel				X				X	X
Liver function tests				X				X	X
Plasma PK*				X				X	X
Serum pregnancy test				X				X	X
Monitor SAE/AE C	X	X	X	X	X	X	X	X	X
Concomitant medication review	X	X		X		X		X	X
Nutritional assessment D	X	X	X	X	X	X	X	X	X
3- day fistula output	X	X	X	X	X	X	X	X	X
Questionnaires								X	X

IRB Study Number: 20170189  
 Version Date: June 16, 2021  
 PI: [name]

NCT02889393

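### The protocol sets no limit, tied to first dose, on the age of the chemistry and liver results that decide eligibility and teduglutide dose

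*Combined protocol and SAP*

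**What the plan says.** Section 5, Eligibility Screening Visit(s), lists a "Chemistry Panel (sodium, potassium, chloride, bicarbonate, blood urea nitrogen, creatinine glucose) if not done in the last 90 days". The liver list ends the same way: "aspartate aminotransferase, lipase, amylase) if not done in the last 90 days". The date from which the 90 days are counted is not given, and "Screening procedures can be completed over several visits".

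The next step is headed "Enrollment within 2 months of signing consent". Its list repeats the inclusion/exclusion check, vital signs, nutritional assessment and fistula output, but has no chemistry or liver panel. The subject is then randomised "to begin teduglutide treatment immediately or to continue standard of care (SOC) treatment". Appendix E agrees: the chemistry and liver rows are marked at Screening and next at "Day 28 Study Visit 3 +/- 1 week", with nothing at Enrollment or Days 7, 14 and 21.

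These results drive decisions. Section 4 excludes subjects whose AST is at least 2 "times upper limit of normal (10-40 U/L"), and sets the same multiple for creatinine (upper limit 1.5 mg/dL). Section 5, Drug Administration, reduces the dose from 0.05 to 0.025 mg/kg/d when creatinine exceeds 1.5 times the upper limit.

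Three other places touch on pre-treatment laboratory work: Drug Administration (baseline data before drug), section 6 (laboratory assessment before drug) and section 8 (blood draws before drug). None gives an age limit.

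**The concern.** An exclusion rule or a dose rule works only if it is applied to a current value. Here the inclusion/exclusion check is repeated at Enrollment, but for AST and creatinine it can be repeated on an old number. A subject whose creatinine has since reached 3.0 mg/dL, or whose AST has reached 80 U/L, could be treated although excluded. A subject whose creatinine has passed 2.25 mg/dL could be given the full dose instead of half.

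Renal function in this population should not be assumed stable over months. Section 9 describes readmission for fistula complications, dehydration among them, as common, and section 6 requires monitoring for volume depletion.

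The safeguard also depends on the randomised sequence, because subjects who start on standard of care have scheduled panels before their first dose. Elsewhere the protocol does tie a test to drug start: section 5 asks for colonoscopy within 6 months before it. The laboratory tests that set eligibility and dose have no such tie.

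**Working it through.** The plan gives no figure for the age of the results at first dose, so there is none to reproduce. The check adds up the calendar windows.

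**Inputs**
- Look-back for chemistry and liver results: 90 days (Eligibility Screening Visit(s)).
- Consent to Enrollment: up to 2 calendar months, which is 59 to 62 days depending on the months.
- Enrollment to first dose, teduglutide-first: taken as 0 days, since the start is immediate.
- Next panel: Visit 3, Day 28 +/- 7, so Day 28 - 7 = 21 to Day 28 + 7 = 35.
- Upper limits of normal: AST 40 U/L, creatinine 1.5 mg/dL (section 4).

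**Thresholds**
- AST exclusion: 2 x 40 = 80 U/L or more.
- Creatinine exclusion: 2 x 1.5 = 3.0 mg/dL or more.
- Half dose: creatinine above 1.5 x 1.5 = 2.25 mg/dL.

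**Age of the deciding result at first dose, teduglutide-first**

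| Case | Sum | Age (days) |
|---|---|---|
| Fresh Screening panel near consent, full 2 months used | 59 to 62 | 59-62 |
| 90-day-old result accepted at a screening visit close to Enrollment | 90 + about 0 | about 90 |
| 90-day-old result accepted near consent, full 2 months used, no routine result in between | 90 + 59 to 90 + 62 | 149-152 |

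Because the reference date for the 90 days is not stated, the second and third cases are both permitted. If Screening and Enrollment fall close together and a fresh panel is drawn, the result is only days old.

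**Standard-of-care-first, for comparison**
- A panel is scheduled at Visit 5, the cross-over visit.
- If that result is not yet back, the Visit 3 panel is 56 - 28 = 28 days old. With the visit windows the range is 49 - 35 = 14 to 63 - 21 = 42 days.

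**Dose consequence, conditional on an undetected rise in creatinine above 2.25 mg/dL before first dose**

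| Days to next scheduled panel | Given at 0.05 mg/kg/d | Due at 0.025 mg/kg/d |
|---|---|---|
| 21 | 21 x 0.05 = 1.05 mg/kg | 21 x 0.025 = 0.525 mg/kg |
| 28 | 28 x 0.05 = 1.40 mg/kg | 28 x 0.025 = 0.70 mg/kg |
| 35 | 35 x 0.05 = 1.75 mg/kg | 35 x 0.025 = 0.875 mg/kg |

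This shows what one missed crossing would mean. It is not an estimate of how often one would occur.

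**The case against.** The strongest reply is that newer results will usually exist and would be used. Subjects come from a Surgical Nutrition service. Section 6 says these tests are normally part of clinical care, and section 5 includes careful fluid and electrolyte management in the standard of care for every subject. The dose rule names no particular panel, so a known later creatinine would govern the dose. Section 9 also lists newly developed renal or hepatic dysfunction, as defined by the exclusion criteria, as possible grounds for withdrawal. Much of this stands. It makes the longest intervals unlikely and limits reliance on an old value once a newer one is known. It does not require a newer result to be on file and reviewed before dosing.

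A second reply is that section 8 already promises blood draws before drug. It does, but without an age limit, and it does not displace the specific 90-day waiver at Screening.

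A reader might also infer three stronger points that the documents do not support:
- That results may be of any age. The 90 days, the 2 months and the immediate start together imply a ceiling of about 150 days.
- That about 150 days is typical. It needs a result accepted at its oldest near consent, the whole 2 months used, and no routine test in between.
- That subjects not on parenteral nutrition are the least protected. Anyone without a result in the last 90 days must have a fresh Screening panel, and section 8 foresees study draws for patients who are not on parenteral nutrition.

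**Conclusion.** The concern holds in a limited form. No limit tied to first dose is set for the results that decide exclusions d(i) and e and the teduglutide dose, and the stated 90-day rule itself permits an outdated one. In the teduglutide-first sequence the result can be about 59 to 90 days old in plausible cases, and 149 to 152 days old at the extreme. The next scheduled check comes at Day 21 to 35 on drug. Subjects who begin with standard of care have panels at Visits 3 and 5.

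This assumes first dose on the day of Enrollment and, for the extreme figure, no intervening routine result. The documents do not say how many subjects would be affected, so no frequency is claimed, and they do not show that any subject would in fact be overdosed. No endpoint or analysis changes. This is a cheap improvement for patient safety, not a flaw in the trial's inference.

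**What to change.** Add one sentence to the Enrollment step and one entry to Appendix E: a chemistry and liver result no older than a short stated limit before first dose must be on file and reviewed. Fourteen days would be one example. The number is a clinical choice for which the documents give no basis. Routine-care results count. The rule is needed for teduglutide-first subjects, but is simplest to apply to everyone before randomisation, so that a subject found ineligible is never allocated. Use that result to recheck exclusions d(i) and e and to choose 0.05 or 0.025 mg/kg/d.

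The cost is at most about 10 standard panels, one per planned subject, and fewer where a recent result exists. First dose may wait a day or so for the laboratory. Some subjects may be found ineligible after Screening, which is what the recheck is for.

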### **Enrollment within 2 months of signing consent**

Inclusion/Exclusion criteria

Vital signs measurements

Nutritional assessment

3-day average fistula output

Complete questionnaires (see additional documents):

1. ASCQ-Me Short Form v2.0 - Social Functioning Impact
2. ASCQ-Me v2.0 - Sleep Impact Short Form

IRB Study Number: 20170189  
Version Date: June 16, 2021  
PI: [name]

NCT02889393

3. Global Health Scale v1.2
4. PROMIS Scale v1.0 - GI Belly Pain
5. PROMIS Scale v1.0 - GI Diarrhea
6. PROMIS Scale v1.0 - GI Nausea and Vomiting
7. PROMIS SF v2.0 - Ability to Participate

Teaching of self-administration of medication

After study enrollment, the subject will be randomly assigned (by a computerized method, using the site 'www.sealedenvelope.com') to begin teduglutide treatment immediately or to continue standard of care (SOC) treatment. The randomization will be performed by a member of the study that is not involved in the informed consent process, and will be enclosed in sequentially numbered opaque envelopes. The envelopes will be given to the PI prior to the enrollment visit. At study visit 5 (day 56), the subject will then cross-over to the opposite treatment assignment. The half-life of teduglutide is 2-3 hours. During the period the subjects are on the "SOC only" treatment arm, the subjects will be given the option to replace some Study visits with Telephone Calls for their convenience. If study visits overlap due to the time window, either visit may be skipped or completed on the same day. Please see information below, and the Study schema.

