**Design**

Open label cross-over pilot study to determine safety and efficacy of teduglutide in patients with ECF. Our planned sample size is 10 subjects randomized and treated with at least 1-dose of study drug .

IRB Study Number: 20170189  
Version Date: June 16, 2021  
PI: [name]

NCT02889393

The primary efficacy end point will be decrease in fistula volume by 20% from baseline 3-day average, as measured by the patient.

The secondary efficacy end points will be cessation of fistula output altogether and health-related quality of life questionnaire score as assessed by the questionnaires (see below) at time points Study Visit 5, 10, and 11 (3 months after end-of-treatment).

Subjects that complete both arms of the study who have a favorable (but incomplete) response and are deemed to be reliable (both as determined by the principal investigator) will be offered an open-label extension during which they will continue to receive teduglutide for up to another 12 months or permanent fistula closure, whichever occurs first.

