**Study Visit 5, Cross-over, (Day 56) (+/- 1 week)**

Collect physical examination  
Collect Vital Signs measurements  
Chemistry Panel (sodium, potassium, chloride, bicarbonate, blood urea nitrogen, creatinine glucose)  
Liver Function tests (total bilirubin, direct bilirubin, alkalkine phosphatase, alanine aminotransferase, aspartate aminotransferase, lipase, amylase)

IRB Study Number: 20170189  
Version Date: June 16, 2021  
PI: [name]

NCT02889393

Plasma PK (Pharmacokinetics)

- Processed according to separate “Sample Processing Procedure”

Serum pregnancy test

Monitor severe adverse events (SAE) and adverse events (AE)

Collect Concomitant medication review

Collect Nutritional Assessment

3-day average fistula volume (3 days immediately preceding study visit)

Collect adjustment of medications and fluids if recorded

Fistula closure (y/n)

Complete Questionnaires (see additional documents)

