**Drug Administration, Dispensation and Disposition**

Once consent is obtained and necessary baseline data collected, the subject will begin receiving teduglutide (0.05 mg/kg/d, for moderate renal impairment defined as serum

IRB Study Number: 20170189  
Version Date: June 16, 2021  
PI: [name]

NCT02889393

creatinine > 1.5 times the upper limit of normal, the dose will be reduced to 0.025 mg/kg/d, administered once daily subcutaneously into the abdomen, thigh, or arm (at approximately the same time each day) for 8 weeks. For enrolled subjects demonstrating a favorable trend and are deemed to be reliable (both as determined by the PI) but still have a fistula at the end of treatment (EOT) or long-term follow-up, the subject will be offered an “open-label” extension whereby they will continue to receive teduglutide at the previous dose for up to another 12 months or permanent fistula closure, whichever occurs first.

Immediately prior to initiating the 8-week period of drug administration, the subject will receive training on how to safely reconstitute and administer the medication. The volume of reconstituted study drug to be administered is a fixed dose of 0.005 mL/kg body weight. Each day, the injection site should be changed. The subject should be dosed at approximately the same time each day. If a subject forgets to take drug, that day’s dose should be administered as soon as possible, even if this is later in the day or evening. Consecutive doses should be separated by approximately 12 hours. Dates of days with missed or incomplete doses are to be reported in the diary. The subject is going to be instructed to bring back all used and unused IP. The IP will then be disposed of per pharmacy SOP. University of Miami Research Pharmacy will be receiving, storing, dispensing, keeping inventory, and disposing the IP for this study as per their standard operating procedures.

Study drug will be packaged, labeled, and delivered to the clinical center by the sponsor or designee. Each study drug kit will contain labeling with the general dosage instructions, storage conditions, expiration date, kit number, and company name. All medication supplied to be used in this study will be manufactured, tested, labeled, and released according to current legal requirements and Good Manufacturing Practice (GMP). Ancillary supply kits containing syringes with needles for injection and reconstitution, sterile water, and alcohol swabs will also be provided.

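### The Day 56 switch has no rule for a standard-care-first patient whose fistula has already closed, and the 20% endpoint then either credits that closure to the teduglutide period or cannot be scored

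*Combined protocol and SAP*

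**What the plan says.** An ECF is the disease-defining entry criterion: "Enterocutaneous fistula (ECF) that could be secondary to volvulus, injury, prior trauma or surgery, or vascular ischemia". No minimum output is set. The treatment schema (Appendix E) marks the inclusion and exclusion check at Screening and Enrollment only.

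Subjects are randomised to start teduglutide at once or to continue SOC. The enrollment section then states: "At study visit 5 (day 56), the subject will then cross-over to the opposite treatment assignment". Visit 5 includes a yes/no closure item and the 3-day average volume, both collected on the day of the switch.

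Closure appears as a limit on treatment only in the extension. The offer there goes to subjects with a favorable trend "but still have a fistula at the end of treatment (EOT) or long-term follow-up", and dosing continues "for up to another 12 months or permanent fistula closure, whichever occurs first". The list under Events Necessitating Withdrawal from Study does not name closure.

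On efficacy, the Design section states: "The primary efficacy end point will be decrease in fistula volume by 20% from baseline 3-day average, as measured by the patient". Cessation of output is a secondary endpoint. Section 7 (Biostatistical Analysis) names one test, an independent-samples t-test comparing baseline with final volume. It does not tie either term to a treatment period.

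**The concern.** A SOC-first subject can reach the first teduglutide dose without the condition under study. This is foreseeable: the protocol's own description of SOC includes occasional surgical repair, and low-output fistulas are eligible.

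Two things are then left open. The first is conduct: the main period is silent on a case that the extension addresses explicitly. The second is attribution: an outcome reached before any drug was given can be carried into the teduglutide period by the choice of baseline. In a study of 10 subjects, one misattributed outcome is visible in any summary. The cessation endpoint has the same weakness, because a closure already present at Visit 5 is recorded again at Visit 10, after teduglutide.

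**Working it through.** The plan has no figure to reproduce, since Section 7 says that no sample size or power calculation was done.

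**Step 1. Scoring one patient.** Take a SOC-first patient with enrollment 3-day average B > 0, fistula closed by Day 56 and still closed at Day 112 (output 0). Percent fall = 100 × (baseline − final) / baseline.

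- Enrollment baseline, Day 112: 100 × (B − 0)/B = 100%. The 20% threshold is met whatever the value of B.
- Enrollment baseline, Day 56: also 100 × (B − 0)/B = 100%. The threshold was already met on SOC alone.
- Day 56 baseline, Day 112: 100 × (0 − 0)/0, which is undefined. The absolute change is 0 mL and no decrease is possible, so the patient cannot be a responder.

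**Step 2. Which baseline applies.** The Design section names a single baseline, and nothing in the visit schedule resets it at Visit 5. The enrollment value is therefore the more natural reading, but the documents do not settle it.

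**Step 3. How likely such a patient is.** Neither the 8-week closure rate on SOC nor the allocation ratio is in the documents. Assume a 1:1 split, so n = 5 of the 10 start on SOC, and let p be the chance of closure by Day 56. The chance of at least one closure is 1 − (1 − p)^5, and the expected number is 5p.

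| Assumed p | 1 − (1 − p)^5 | Chance of at least one | Expected number |
|---|---|---|---|
| 2% | 1 − 0.904 | about 10% | 0.10 |
| 5% | 1 − 0.774 | 23% | 0.25 |
| 10% | 1 − 0.590 | 41% | 0.50 |
| 20% | 1 − 0.328 | 67% | 1.00 |
| 30% | 1 − 0.168 | 83% | 1.50 |

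If chance puts 4 or 6 subjects in the SOC-first group, the extremes become 1 − 0.98^4 = 8% and 1 − 0.7^6 = 88%.

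**Step 4. Effect on a summary.** With the enrollment baseline, each such patient adds 1/10 = 10 percentage points to a responder proportion among all 10, or 1/5 = 20 points within the SOC-first sequence. With the Day 56 baseline, the patient either leaves the denominator or counts as a non-responder. The plan does not say which.

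**The case against.** The strongest objection is that false credit is not established. The drug administration section says "Once consent is obtained and necessary baseline data collected, the subject will begin receiving teduglutide", which can be read as a baseline taken just before the first dose. On that reading the SOC-first patient has a zero baseline and cannot be a responder. This stands. A reader might infer that a patient closed on SOC necessarily scores as a teduglutide responder, but the documents support that only if baseline is the enrollment value.

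Second, a within-patient comparison of periods would show no teduglutide benefit for this patient, because the threshold is already met at Day 56. That is correct, but no such comparison is planned. The one named test sets baseline against final volume, and for a SOC-first patient the natural final value follows teduglutide. It is also true that Section 7 specifies no responder analysis. The 10-point figure therefore describes the summary that the endpoint implies, not one that the plan sets out.

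Third, one might say that the protocol contradicts itself on treating a subject without a fistula. That goes too far. Different conditions in the cross-over and in an optional extension are not a contradiction, and no sentence says that a closed-fistula subject must be dosed. The withdrawal section also leaves room for a decision by the investigator or a medical decision. These routes are discretionary, neither names closure, and neither settles the scoring.

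Fourth, the Visit 5 closure item is not idle: it feeds the cessation endpoint and would identify the event as occurring before drug. What is missing is a rule that uses it for dosing or for period attribution.

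Finally, the exposure could be presented as a demonstrated neoplastic hazard. The protocol calls that risk theoretical and says that trials have not shown it, so the point does not rest on it.

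**Conclusion.** The gap is real and the consequence is conditional. Followed as written, the protocol moves every SOC-first subject to teduglutide at Day 56 without reference to fistula status, and the plan cannot score a subject who has closed by then in a sound way. Under the enrollment baseline a lasting SOC closure becomes a 100% fall after teduglutide. Under a Day 56 baseline the percent change does not exist.

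The size rests on three assumptions: about five SOC-first subjects, an assumed 8-week closure rate, and closure that lasts to Day 112. Over closure rates of 2% to 30% the chance of at least one such subject runs from about 10% to 83%. Subjects enter with a fistula still open and continue the same care, so the lower rates cannot be dismissed. Because the event may not occur and the study is an unpowered 10-subject pilot, this is a correction worth making rather than one on which the whole trial depends.

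**What to change.** 1. Reconcile the unconditional Day 56 switch in the enrollment section with the closure limits that the Design and drug administration sections state for the extension. The protocol should then give one explicit rule for a subject whose fistula has closed by Visit 5. Which rule to adopt is the sponsor's clinical decision.

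2. In Section 7, define baseline and final measure for each treatment period. State that closure before the first teduglutide dose is an SOC-period outcome and is never counted as a teduglutide response on either the 20% endpoint or the cessation endpoint. This is needed whichever clinical rule is chosen.

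The cost is a sentence in the protocol and a short scoring rule. The closure item and the 3-day volume are already collected at Visit 5, so no visit or measurement is added. The downside is that such a subject may contribute no teduglutide-period efficacy value, which should be reported as a count.
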